| FSH Measurement (Female Participants of Non-Childbearing Potential Only) | X | | | | | | | | |
| 12-Lead ECG ^e | X ^b | X | X | X | X | X (at Cycles 4 and 5 only) | X | | |
| ECHO or MUGA with EF | | As clinically indicated by Investigator | | | | | | | |
| Vital Signs | X | X | X | X | X | X | X | | |
| PK Sampling ^f | | X | X | X | X | X (at Cycles 4 and 5 only) | | | |
| Tumor Evaluation (per RECIST v1.1) | X | Every 8 weeks (± 7 days) during the first 12 months and every 12 weeks (± 7 days) thereafter until disease progression, death, withdrawal of consent, loss to follow-up, or participant/legally acceptable representative decision, and at EOT/ED (as applicable). If PR/CR is reported, confirmation of response is required; confirmatory assessment should be performed ≥ 4 weeks after response is first documented. ¹ | | | | | | | |
| Whole-Body Bone Scan ^g | X | Every 8 weeks (± 7 days) for the first 12 months, then: -If initial bone scan is positive for bony lesion, every 12 weeks thereafter, OR -If initial bone scan is negative for bony lesion, bone scan can be done annually or per Investigator standard of care. | | | | | | | |

| Procedure | Screening | Treatment Phase | | | | | | Post-Treatment Follow-up Phase | |
|---|--|--|--|----------|----------|-------------------|--|-----------------------------------|--------------------------|
| | | Cycle 1 | | Cycle 2 | Cycle 3 | Subsequent Cycles | EOT/ED (as applicable) | Safety Follow-up | Survival Follow-up Phase |
| Study Day(s) | D-42 to D-1 | D1 | D15 | D1 | D1 | D1 | Within 15 days after last dose of lerociclib | Last dose of lerociclib + 30 days | Every 12 weeks |
| Visit Window (days) | - | - | ± 2 days | ± 2 days | ± 2 days | ± 2 days | - | + 5 days | ± 7 days |
| Lerociclib Administration/Accountability | | Twice daily continuously in 28-day cycles ^a | | | | | | | |
| Letrozole Administration ⁱ | | Once daily continuously in 28-day cycles | | | | | | | |
| Fulvestrant Administration ⁱ | | X | X | X | X | X | | | |
| Goserelin Administration ^j | X (goserelin dosing required for ≥ 28 days prior to study entry) | X (determined as date of participant's last goserelin dose + 28 days ^l) | q28d after goserelin C1D1 for the individual participant | | | | | | |
| AE/SAE Review | X (continuous from Screening through 30 days after last study intervention dose) | | | | | | | | |

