While receiving lerociclib, participants will undergo imaging assessments (via CT of the chest/abdomen/pelvis with contrast or MRI with gadolinium) every 8 weeks for the first 12 months, then every 12 weeks thereafter. All participants will undergo a bone scan at baseline and annually thereafter (or as per the Investigator's standard of care). If bone disease is identified, participants will require whole-body bone scans every 8 weeks for the first 12 months and then every 12 weeks thereafter.

Optional imaging modalities include a brain CT/MRI (if brain lesion[s] indicated at Screening), CT/MRI for any disease outside the chest/abdomen/pelvis (if lesion[s] identified at Screening), or skin color photography (if skin lesion[s] identified at Screening) every 8 weeks during the first 12 months, then every 12 weeks thereafter.

Participants will continue therapy until disease progression as determined by the Investigator per RECIST v 1.1, unacceptable toxicity, withdrawal of consent, start of a new anticancer treatment, discontinuation of the participant by the Investigator, or termination of the study by the Sponsor, whichever occurs first.

Following disease progression, participants will only be followed for survival, and will no longer require any scheduled assessments beyond that timepoint. Survival status will be assessed every 12 weeks regardless of the participant's reason for discontinuing study treatment.

Safety monitoring (AE/SAE monitoring, clinical laboratory tests, vital signs, 12-lead ECGs, physical examination), serial blood samples for PK, tumor biopsies, and bone scans will be performed at the timepoints specified in the study SoA ([Table 1](#)).

The study is anticipated to last for a total of approximately 48 months. This assumes 12 months to complete participant recruitment and a median PFS of 24 months, plus an additional 12 months for further monitoring.

An independent DSMB will be set up to periodically review and evaluate the accumulated study data for participant safety and for study conduct and progress, and to make recommendations to the Sponsor concerning the continuation of the study (as detailed in [Section 7.4](#)).

This study will be conducted in compliance with the protocol, GCP, and applicable regulatory and IRB/IEC requirements.

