- The Sponsor or legal representative of the Sponsor requests the participant to withdraw.
- The participant has documented disease progression.
- The participant is lost to follow-up.
- The participant exhibits any evidence of drug abuse.
- Permanent study treatment discontinuation is judged by the Investigator to be in the best interest of the participant.
- The participant withdraws consent.
- The Sponsor makes the decision to terminate the site or study.

In the event of a participant discontinuing from IMP (lerociclib) treatment (without withdrawal of consent from the study), that participant should be strongly encouraged to complete all protocol-scheduled assessments—to include the Safety Follow-up Visit 30 days after the last dose of lerociclib and the Post-Treatment Follow-up Phase (which includes a Survival Follow-up Phase that is to continue until at least 50% of enrolled participants have died).

A participant who discontinues from study treatment for reasons other than PD will have a CT or MRI scan performed during the Post-Treatment Visit if that participant has not had a scan performed within the prior 4 weeks.

The Investigator will document the reason for each participant's discontinuation from lerociclib treatment on the applicable eCRF page. When a participant's discontinuation from lerociclib is due to either an SAE or a Grade 3 or 4 toxicity considered to be related to the IMP, the Investigator should follow the event until resolution, stabilization, or it is deemed that further recovery is unlikely. Data on these events should be collected on the AE form in the eCRF.

In the event that a participant discontinues from lerociclib due to an AE or pregnancy, the Investigator should notify the Sponsor Medical Monitor or Pharmacovigilance representative by email within 24 hours of IMP discontinuation.

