8.1.1. Antitumor Activity Assessments

For tumor assessment, all sites of disease, including but not limited to the chest, abdomen, and pelvis, should be assessed radiologically by CT or MRI at Screening and every 8 weeks for the first 12 months, then every 12 weeks until the occurrence of disease progression ([Table 1](#)). A central imaging vendor will be used to collect and hold these images for possible future review by independent radiologists. Objective response data collected for the clinical study report will be based on Investigator assessment.

Scans (CT or MRI) obtained prior to informed consent will not need to be repeated if performed within 28 days prior to dosing. Radionuclide bone scans shall be performed at Screening for all participants and annually thereafter or as clinically indicated. All participants with a CR must have a radionuclide bone scan as part of confirmation of the CR. Additional scans may be obtained at the discretion of the Investigator, if clinically indicated.

Participants with bone-only disease will be followed with bone scans only at Screening and every 12 weeks on treatment.

If a participant shows a radiological response (CR or PR), a confirmatory radiological assessment will be performed at least 4 weeks after the response was first noted. Participants who have a confirmed CR will have a bone scan to confirm absence of bony metastases.

For all participants (1L or 2L populations), if they remain on therapy for 12 months following enrollment, the timing of CT or MRI scans should be lengthened to every 12 weeks.

The same method of assessment (CT or MRI) should be used to characterize tumors at Screening and at all follow-up assessments. If PET is used, it should also be accompanied by spiral CT or MRI.

Investigators should follow RECIST v1.1 Guidelines ([Eisenhauer 2009](#)) for tumor assessments and determination of overall response.

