4.10.1.3 Visit Windows

Analysis visit windows will be created based on the schedule of assessments in the protocol (Appendix 6.1) as shown below. Any visits outside the visit window will be considered “Unscheduled” and not summarized at a scheduled visit. If multiple records are mapped to the same visit, the one closest to the date of the scheduled assessment will be used. If there is an equal distance from the date of the scheduled assessment, the latest record will be used.

| Visit | Study Day Window |
|------------------|--|
| Screening | [-42, -1] |
| Cycle 1 Day 1 | 1 |
| Cycle 1 Day 15 | [13, 17] |
| Cycle 2 Day 1 | [27, 31] |
| ... | [expected day – 2 days, expected day + 2 days] |
| EOT/ED | [last dose day, last dose + 15 days] |
| Safety Follow-up | [last dose + 25 days, last dose + 35 days] |

For tumor evaluations, the following windows will be implemented:

| Visit | Study Day Window |
|---|--|
| Screening | [-42, -1] |
| Cycle 3 Day 1 | [50, 64] |
| Every 2 cycles (8 weeks) during first 12 months and every 3 cycles thereafter (12 weeks) until EOT/ED | [expected day – 7 days, expected day + 7 days] |
| EOT/ED | [last dose day, last dose + 15 days] |

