4.10.3.2 Progression-free Survival (PFS)

Progression-Free Survival (PFS) is defined as the time to PFS event from first exposure to lerociclib. PFS event is defined as PD (per RECIST v1.1 as assessed by the investigator) or death due to any cause, whichever comes first. For participants without death or disease progression, PFS will be censored at the date of the last valid RECIST assessment unless otherwise stated. PFS duration will be calculated as

$$\text{Date of observation} - \text{Date of first exposure to lerociclib} + 1$$

where date of observation is the earliest of death, progression, or censoring.

PFS events and censoring rules, such as initiation of disallowed anticancer therapy, are defined below in Table 2.

All valid RECIST assessments after start of treatment will be used in the PFS analysis regardless of whether they were collected as part of scheduled or unscheduled visits. RECIST assessments based on scans performed after the end of lerociclib therapy will be used in the analysis of PFS if prior censoring events have not been observed.

Table 2 Censoring Rules for Progression-Free Survival

| Situation | Outcome | Date of Event/ Censoring |
|--|---------|---|
| PD or death, whichever occurred first, before exposure to subsequent antineoplastic therapy, withdrawal of consent, loss to follow up, data cutoff, or end of study. | Event | Earliest date of documented progression or death |
| No baseline disease assessment | Censor | Date of first exposure |
| No valid post-baseline tumor assessment | Censor | Date of first exposure |
| PD or death immediately after missing ≥ 2 consecutive scheduled tumor assessment | Censor | Date of last valid tumor assessment prior to the missing tumor assessments |
| No PD or death on or before 
 Database cut End of study Start of new antineoplastic therapy | Censor | Date of last tumor assessment on or prior to earliest censoring event listed in first column of this row. |

Descriptive summaries of time to event data will include median, twenty-fifth and seventy-fifth percentiles, and associated 2-sided 95% CIs based on Kaplan-Meier methods. Survival estimates along with corresponding 95% CIs using the log-log transformation will be provided at certain intervals as data allows.

A Kaplan-Meier plot will be presented and will include the number of participants at risk over time by line of therapy. No formal statistical hypothesis will be tested.

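### After lerociclib is stopped without progression, the documents disagree on whether imaging continues, so the same later death can be a PFS event or be censored

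*Protocol*

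**What the plan says.** The point concerns participants who come off lerociclib for a reason other than progression and have not withdrawn consent.

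**Imaging tied to treatment.** Protocol 4.1 opens its imaging paragraph with "While receiving lerociclib, participants will undergo imaging assessments"; the synopsis and SAP 3.1 use the same condition. SAP 4.10.1.3 defines the tumor windows as "Every 2 cycles (8 weeks) during first 12 months and every 3 cycles thereafter (12 weeks) until EOT/ED", and the EOT/ED window closes 15 days after the last dose.

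**Imaging run to progression.** The tumor evaluation row of the Schedule of Activities (SoA) continues "thereafter until disease progression, death, withdrawal of consent, loss to follow-up, or participant/legally acceptable representative decision, and at EOT/ED". Protocol 8.1.1 asks for scans "every 8 weeks for the first 12 months, then every 12 weeks until the occurrence of disease progression". SAP 3.2.2 repeats the SoA rule. SAP 4.10.3.2 adds that "RECIST assessments based on scans performed after the end of lerociclib therapy will be used in the analysis of PFS", provided no censoring event came first.

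**In between.** Protocol 7.1.1 keeps the participant in the study for safety and survival follow-up and encourages completion of all scheduled assessments. It also says: "A participant who discontinues from study treatment for reasons other than PD will have a CT or MRI scan performed during the Post-Treatment Visit", if none was done in the prior 4 weeks. Protocol 7.1.2, by contrast, takes a participant out of the study once lerociclib has been off for more than 14 days.

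**PFS coding.** In SAP Table 2, progression or death before new antineoplastic therapy, consent withdrawal, loss to follow-up, data cutoff or end of study is an event. Another row censors a progression or death that comes immediately after two or more consecutive missed scheduled assessments, at the last valid scan before the gap. SAP 4.10.3.4 applies the same rules to DOR.

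**The concern.** Table 2 depends on the word scheduled, and the documents give that word two meanings once lerociclib stops. On the SAP windows, nothing is scheduled after EOT/ED, so nothing can be missed. On the SoA, scans stay due until progression, so an unscanned participant soon accumulates two missed assessments. One patient history then fits both the event row and the censoring row, and no precedence is stated.

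There is also a conduct risk. A site that follows 4.1 may stop scanning at drug stop. A living participant with no documented progression is then censored at the last scan. If people who stop are likelier to progress than those who stay on, that censoring is informative and the Kaplan-Meier curves for PFS and DOR sit too high. With no comparator arm, those curves are the PFS and DOR results, so their event definition should not depend on the section a site or programmer happened to read.

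**Working it through.** **1. The same death under both readings.** Inputs: 8-weekly scans in the first 12 months (SoA), a ±7-day window, and the missed-assessment row of Table 2. Assume a participant stops for toxicity at week 16, has a scan that week showing no progression, starts no new anticancer therapy, and has no further scan.

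| Death at | Scans passed since stop (SoA reading) | Scans end with lerociclib | Scans run to progression |
|---|---|---|---|
| Week 30 | 24 | Event, week 30 | Event, week 30 |
| Week 34 | 24, 32 | Event, week 34 | Censored, week 16 |
| Week 40 | 24, 32 | Event, week 40 | Censored, week 16 |

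The readings part once two scheduled scans have passed. For the week-40 death the recorded time differs by 40 − 16 = 24 weeks and the status flips. If new antineoplastic therapy starts before the death, Table 2 censors under both readings and the contrast disappears. If 7.1.2 has removed the participant from the study, it is also unclear whether the death falls after the end of participation.

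**2. Size of the possible bias.** The documents state no precision for PFS. The only PFS planning figure is the 24-month median, which serves the study length: 12 + 24 + 12 = 48 months, as stated. The share stopping without progression and the hazard after stopping are not in the documents. They are assumed here: 10–20% stopping by 12 months, and a hazard ratio (HR) after versus before stopping of 1 to 3. The 24 months is used, also as an assumption, as the on-drug median.

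Let λ = ln 2/24 = 0.02888 per month, μ = −ln(1 − p)/12 where p is the proportion stopping by 12 months, and d = λ + μ − λ·HR. With everyone followed to the event,

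S(t) = exp(−(λ+μ)t) + μ·exp(−λ·HR·t)·[1 − exp(−d·t)]/d.

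If every stopper is censored at the stop, Kaplan-Meier returns exp(−λt): median 24 months, 50% at 24 months.

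Mid case, p = 15% and HR = 2: μ = 0.01354 and d = −0.01534. Then S(24) = 0.3612 + 0.01354 × 0.25 × 29.01 = 0.3612 + 0.0982 = 0.46, and the median is 21.6 months. Censoring at stop overstates the median by 24.0 − 21.6 = 2.4 months and 24-month PFS by about 4 points.

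Median PFS with full follow-up, simulating 400,000 participants per scenario (about 24.0 in every scenario when censored at stop):

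| Stop by 12 months | HR 1 | HR 1.5 | HR 2 | HR 3 |
|---|---|---|---|---|
| 10% | 24.0 | 22.9 | 22.3 | 21.4 |
| 20% | 24.0 | 22.1 | 21.0 | 19.4 |

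The closed form agrees to within 0.1 month. The overstatement runs from 0 to 24.0 − 19.4 = 4.6 months (4.66 from the closed form in that last cell), and is zero at HR 1.

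**3. Why this is a worst case.** The calculation assumes that no stopper is scanned again at any site and that no death after stopping is counted. Its full-follow-up figure also ignores Table 2's censoring at new antineoplastic therapy, so better scanning could not recover all of the gap.

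**The case against.** The strongest reply is that the documents lean towards the SoA. Protocol 8.1 places the timing of all efficacy assessments there, Section 8 makes adherence to it mandatory, and 7.1.1 and 7.2.1 ask that people who stop early still complete the planned assessments. Protocol 4.1 itself releases participants from scheduled assessments after progression, and making scans a duty while on drug does not strictly say they end with it. This stands as a guide to probable intent. It does not settle Table 2, because the SAP's own tumor windows stop at EOT/ED.

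A reader might infer that the SAP censors PFS at treatment stop. It does not: Table 2 has no such row, and 4.10.3.2 admits all valid assessments, scheduled or not, including those after lerociclib. The windows exclude no scan from PFS; they bear only on what counts as missed. Bias needs both lapsed scanning and prognosis-related stopping.

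A reader might also infer that questionnaires end at stopping. No section says so. They run to progression and at EOT; the only gap is that they fall on Day 1 of a cycle, and cycle days are counted from lerociclib dosing. They do not enter PFS.

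On stakes, the primary endpoint is adverse-event incidence, PFS is untested, and no comparison with other CDK4/6 inhibitors is planned. The primary analysis comes about 6 months after the last first dose. With 12 months of recruitment, follow-up then is about 6 to 18 months, so a 24-month figure would not yet be directly observed. All of this stands and limits the weight of the point.

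**Conclusion.** The inconsistency is in current text and should be corrected before database lock. For a participant who stops lerociclib without progression, starts no new anticancer therapy, and dies after two scheduled scan dates have passed without a scan, the plan supports both an event at death and censoring at the last scan. DOR inherits the ambiguity. This part follows from the text and rests on no assumption about rates.

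The upward bias in PFS and DOR is conditional, and its size cannot be derived from the documents. Under the assumed 10–20% stopping by 12 months and post-stop hazard ratios of 1 to 3, the worst-case overstatement of the median is 0 to about 4.6 months. It should be read as an upper bound, not a forecast. No alpha, power or sample-size statement is affected.

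**What to change.** - In the synopsis, Protocol 4.1 and SAP 3.1, state that imaging runs from first dose until progression whatever the treatment status, matching the SoA and 8.1.1.
- In SAP 4.10.1.3, extend the tumor windows past EOT/ED on a calendar counted from first dose, and list the weeks. Twelve months is not a whole number of 8-week intervals (52/8 = 6.5), so the switch to 12-weekly scans needs a stated date.
- In SAP Table 2, define a scheduled tumor assessment by that calendar, and state which row prevails when a death meets both the event row and the missed-assessment row.
- Add a sensitivity analysis of PFS and DOR that counts every progression and death regardless of missed scans.
- Reconcile Protocol 7.1.1 and 7.1.2 on whether a participant remains in the study after stopping. This is a consistency request and takes no view on the clinical rule.
- Optionally, clarify when questionnaires fall due after EOT.

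The cost is wording in two documents and one extra analysis. Sites that stopped imaging at EOT would perform scans the SoA already lists; no new procedure is added.
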